##### 6.8.1. Questionnaires

Questionnaire results will be analyzed as described in sections 4.1 and 4.2.1.

Wherever not specified explicitly, the following comparisons will be listed by subjects for each questionnaire and also be tabulated by treatment.

- Scores at V1, V3, V4, and V5
- Score difference between V1 and V4

- Score difference between V4 and V5
- Score difference between V1 and V5

#### **6.8.1.1. DTQ**

For DTQ both the change scores and the status scores will be analyzed. For the change scores, the same ANCOVA as for the primary analysis will be used. All other comparisons will be analyzed using t-tests.

Difference scores as described in section 6.8.1 will be performed both on the “now” scores and on the “change” scores, even though the latter ones already reflect differences/changes.

#### **6.8.1.2. HbA1c laboratory value**

Difference of HbA1c between V4 and V2

$$\text{Diff HbA1c} = \text{HbA1c}(V4) - \text{HbA1c}(V2)$$

will be tested hierarchically as described in section 2.7. An Analysis of Covariance (ANCOVA) with HbA1c difference as independent variable and the HbA1c values at V2 and the site as covariates will be utilized.

Additionally, HbA1c values at all visits and the differences between the value obtained at a given visit and the value obtained at V2 will be listed and tabulated by treatment.

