## Protocol Outline

For comprehensive details, please refer to the respective sections.

Study Title:	Patient-Reported Outcomes with the Accu-Chek® Solo Micropump System vs. Multiple Daily Injection Therapy vs. mylife OmniPod® in People with Type 1 Diabetes
Short Name	PRO Solo Study
Investigational Device:	Accu-Chek® Solo micropump system
Other Study Devices:	
 
- Intensified therapy with multiple daily injections (MDI)
 
- mylife™ OmniPod® Insulin Management System (Insulet Corporation)
 

Research Question/ Working Hypothesis:	
Assessment of treatment satisfaction in patients with type 1 diabetes comparing Accu-Chek® Solo to standard therapy via MDI and to mylife™ OmniPod®.
 
First Null hypothesis: There is no difference in treatment satisfaction between Accu-Chek® Solo and MDI.
 
First Alternative hypothesis: Treatment satisfaction is higher with Accu-Chek® Solo than with MDI.
 
Second Null hypothesis: There is no difference in treatment satisfaction between Accu-Chek® Solo and mylife™ OmniPod®.
 
Second Alternative hypothesis: Treatment satisfaction is higher with Accu-Chek® Solo than with mylife™ OmniPod®.

Primary Objective:	To compare treatment satisfaction with Accu-Chek® Solo versus MDI and versus mylife™ OmniPod® assessed by Diabetes Technology Questionnaire (DTQ).
Secondary Objectives:	
To evaluate
 
 
• Mean HbA1c change difference between treatment groups at end of study
 
• Therapy relevant examination and diary parameters
 
• The answers of additional questionnaires measuring psychological parameters relevant in diabetes therapy
 
• Therapy relevant parameters from data download from BG-meter or respective patch pump, e.g. bolus frequency
 
• Device parameters
 

Indication	Type 1 diabetes mellitus
Target Population	Age ≥ 18 years
Number of Subjects	180 subjects, 60 subjects in each treatment group
Number of Sites	10-20
Countries	Austria, Germany, Poland, and UK
Study Design:	
Prospective, multinational study where adults ≥ 18 years will be randomly allocated (1:1:1 ratio) to
 
Group A: Continuous subcutaneous insulin infusion (CSII) with Accu-Chek® Solo micropump system for 26 weeks.
 
or

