### 11.6 Secondary Objective(s) Analysis

For subjects from groups B (starting with MDI) and C (starting with mylife™ OmniPod®), who will all use the Accu-Chek® Solo micropump after week 26, the change in DTQ score between week 26 and week 39 will be analyzed.

Additionally, the following parameters will be tested. More parameters may be specified in the statistical analysis plan (SAP). Both pairwise tests (Accu-Chek® Solo versus MDI and Accu-Chek® Solo versus mylife™ OmniPod®) and simultaneous analyses of all three treatment alternatives will be performed where applicable, e.g. using an Ancova with treatment arm as independent variable. Baseline adjustment will be performed where applicable. Details will be specified in the SAP.

- Psychological parameters that describe or affect therapy:
  - Treatment satisfaction with Accu-Chek® Solo system vs. mylife™ OmniPod®, measured by the difference in the Diabetes Technology Questionnaire (DTQ) change score after 26 weeks.
  - Diabetes-related Emotional Distress assessed by PAID-5.
  - Device satisfaction
  - Device and Treatment Preference
- Physical parameters that describe therapy changes or success:
  - HbA1c
  - Change in weight and BMI
  - Glycemic variability
- Therapy parameters that describe therapy changes or may affect the results
  - Indication for commencement of CSII
  - Type of insulin used
  - Total daily insulin dose (TDD)

- Total daily basal insulin dose (TBD)
- Average number of SMBGs per day
- Frequency of hypoglycemic events
- Frequency of hyperglycemia
- Frequency of consultations between scheduled visits, emergency and call center calls, hospitalizations and absenteeism from work/school
- Device specific parameters that may affect user acceptance
  - Number of pods/ infusion assemblies falling off prematurely
  - Average infusion assembly usage time
  - Number, type and intensity of skin reactions
- Parameters that may affect socio-economic acceptance
  - Insulin amount left in device at reservoir change / device discard
  - Amount of waste, inferred by total material consumption
- Subject withdrawal
  - It will be tested whether there is a bias in the fraction of subject withdrawal among the different treatment arms
- Descriptive evaluation:
  - Accu-Chek® Solo micropump system: Training Satisfaction

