## 2.5. Primary efficacy endpoints

The primary goal of the study is to assess, if treatment satisfaction in the Accu-Chek® Solo group (Group A) increases in comparison to the group using MDI (Group B) and to the mylife™ OmniPod® group (Group C). Change in treatment satisfaction will be assessed by Part 1, "Impact and Satisfaction" of the Diabetes Technology Questionnaire (DTQ). This question-naire

consists of two parts of identical questions, the status part (“Is this a problem now?”) and the change part (“How has it changed compared to your treatment before the study?”). For the current study, the change part (“How has it changed compared to your treatment before the study?”) will be used as primary variable with the status part as covariate.

The status part can be answered with a rating between 1 (very much) and 5 (not at all), the change part with a rating between 1 (much worse) and 5 (much better). For both parts, the sum of all individual answer scores will be used for analysis.

The change score as dependent variable will be analyzed with an Analysis of Covariance (ANCOVA) with group as independent variable and the status (“Is this a problem now?”) answers of the DTQ assessed at Visit 1 (V1) and the site as covariates.

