## 2.7. Hierarchical Testing Procedure

The comparisons between the Accu-Chek® Solo group and MDI and between the Accu-Chek® Solo group and the mylife™ OmniPod group will be performed hierarchically. Only if the comparison between the Accu-Chek® Solo and the MDI group will show a statistically significant difference, the comparison between the Accu-Chek® Solo and the mylife™ OmniPod® group will also be performed.

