#### **6.6. Analysis of Primary Endpoint DTQ**

The primary endpoint of this study is the change in DTQ part 1 as described in 2.5. A hierarchical procedure as described in section 2.7 will be applied. The comparison between Accu-Chek® Solo and mylife™ OmniPod® will only be performed, if the Null Hypothesis of no difference between Accu-Chek® Solo and MDI can be rejected.

The comparisons will be performed using an ANCOVA with the DTQ score as dependent variable and treatment arm, baseline DTQ score, and site as covariates. SAS proc GLM will be used for the analysis.

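### The HbA1c ANCOVA in SAP 6.8.1.2 is misstated: the outcome is labelled the independent variable and treatment arm is left out, so the sentence should be corrected to match the intended model

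*SAP*

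**What the plan says.** SAP 6.8.1.2 defines the HbA1c difference as the V4 value minus the V2 value and says that it "will be tested hierarchically as described in section 2.7". The next sentence gives the model: an ANCOVA "with HbA1c difference as independent variable and the HbA1c values at V2 and the site as covariates will be utilized". Neither document states the HbA1c model anywhere else.

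The cross-referenced SAP 2.7 sets an order of testing: "The comparisons between the Accu-Chek® Solo group and MDI and between the Accu-Chek® Solo group and the mylife™ OmniPod group will be performed hierarchically", with the OmniPod comparison conditional on a significant MDI comparison. It contains no model.

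Three other places bear on the intended model:

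- SAP 2.5, for the primary DTQ endpoint: "The change score as dependent variable will be analyzed with an Analysis of Covariance (ANCOVA) with group as independent variable", with the V1 status answers and site as covariates.
- SAP 6.6, again for the DTQ: an ANCOVA "with the DTQ score as dependent variable and treatment arm, baseline DTQ score, and site as covariates".
- Protocol 11.6, for secondary parameters including HbA1c: pairwise and three-arm analyses, "e.g. using an Ancova with treatment arm as independent variable. Baseline adjustment will be performed where applicable. Details will be specified in the SAP".

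The Protocol Outline words the HbA1c objective as a between-group comparison, the mean HbA1c "change difference between treatment groups at end of study".

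**The concern.** Two things are wrong in one sentence. The quantity under study is called the independent variable, which leaves the model without a named outcome. The factor whose effect is to be tested does not appear among the terms. The preceding sentence promises two between-arm tests, and the model statement contains nothing that could deliver them.

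The wording matters because this is the only specification of the test. Protocol 11.6 offers its ANCOVA as an example and leaves the detail to the SAP, so 6.8.1.2 is where that detail should stand. SAP 6.1 also restricts statistical testing to what the document specifies explicitly. The study is unblinded (SAP 2.2), and an analysis is planned once all subjects have passed V4 or withdrawn (SAP 2.11 and 6.5). A model completed by inference after that point is less cleanly prespecified than one written out beforehand.

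**Working it through.** **Figures in the plan.** No sample size or power is stated for HbA1c. The only sample size is for the DTQ (SAP 2.8): difference 110 − 90 = 20, SD 30, two-sided alpha 0.05, power 90%. The t-test solution is 48.26, rounded up to 49 per group, and 49 / (1 − 0.18) = 59.8, rounded up to 60. The plan's figures reproduce, and nothing below changes them.

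**Step 1: read the sentence literally.** The terms named are HbA1c difference (called independent), V2 HbA1c and site. No dependent variable is named, so no model can be programmed from this alone.

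**Step 2: correct only the label.** Let D be HbA1c(V4) − HbA1c(V2). With D as the dependent variable, the listed terms give

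E[D] = μ + β × HbA1c(V2) + site effect.

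Two subjects at the same site with the same V2 value have the same expected D whichever arm they are in. There is no parameter for A − B or A − C (A = Solo, B = MDI, C = OmniPod).

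**Step 3: add arm.**

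E[D] = μ + arm effect + β × HbA1c(V2) + site effect.

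Three arms give 3 − 1 = 2 degrees of freedom, which carry the contrasts A − B and A − C.

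**Step 4: count the parameters.** Inputs are 180 subjects in three arms (SAP 2.2) and 20 sites (SAP 2.2 says approximately 20). Site is taken as a class variable, which is an assumption.

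| Term | Listed terms only | With arm added |
|---|---|---|
| Arm | 0 | 2 |
| V2 HbA1c | 1 | 1 |
| Site | 19 | 19 |
| Residual | 180 − 1 − 1 − 19 = 159 | 180 − 1 − 2 − 1 − 19 = 157 |

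A fit to simulated data with this layout returned these degrees of freedom: no arm parameters in the first model and two in the second. The simulated HbA1c values are invented and carry no information about the trial. With 10 sites, the lower end of the protocol's range, the residual degrees of freedom would be 169 and 167, and the arm row would not change.

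**Step 5: compare with the parallel DTQ model.**

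| Element | DTQ (SAP 2.5) | DTQ (SAP 6.6) | HbA1c (SAP 6.8.1.2) |
|---|---|---|---|
| Dependent variable | Change score | DTQ score | Not named |
| Treatment term | Group | Treatment arm | Not listed |
| Baseline covariate | V1 status | Baseline DTQ | V2 HbA1c |
| Site | Yes | Yes | Yes |
| Label given to the outcome | Dependent | Dependent | Independent |

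The HbA1c sentence follows the pattern of SAP 2.5, apparently with the words that name the outcome as dependent and group as independent run together or lost.

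**The case against.** The strongest reply is that nobody would be misled. The sentence before the model, through SAP 2.7, names the two comparisons. SAP 6.8 says that the secondary endpoints are analysed by study arm and visit. Protocol 11.6 names treatment arm as the independent variable and foresees baseline adjustment. SAP 2.5 supplies an almost identical template. The sentence cannot be run literally, so a programmer would have to resolve it, and every neighbouring statement points to the same terms. A silent wrong result is unlikely.

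Most of this stands, and it limits the consequence. It does not make the sentence correct. SAP 2.7 supplies an order and no model, and protocol 11.6 supplies only an example. Inference also leaves one detail open: protocol 11.6 foresees both pairwise and three-arm analyses, so adding arm does not by itself say whether both contrasts come from a single three-arm fit.

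A reader might infer something stronger: that the hierarchical HbA1c test cannot be carried out, or that the leading secondary endpoint has no valid analysis. The documents do not support either reading. The missing parameters are a property of the listed terms and not of the data; V2 and V4 HbA1c, arm and site are all collected. No document ranks the secondary endpoints. HbA1c comes first in the Protocol Outline, but protocol 4.2 and 11.6 and SAP 2.1 list it after the psychological parameters.

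**Conclusion.** The point holds as a drafting error in an operative analysis rule. The HbA1c ANCOVA in SAP 6.8.1.2 mislabels its outcome, names no dependent variable and omits treatment arm. Its listed terms provide 0 of the 2 arm degrees of freedom that the comparisons in the same section require, and changing one word does not cure that.

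The effect is confined to how one secondary endpoint is specified. The primary analysis, the alpha level and the sample size do not change, and a statistician would very likely recover the intended model. That rests on reading SAP 2.5 and 6.6 as the pattern for HbA1c, which the shared covariate structure and the reference to SAP 2.7 support.

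**What to change.** Replace the model sentence in SAP 6.8.1.2 with wording such as:

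> *The HbA1c difference (V4 − V2) is the dependent variable of an ANCOVA with treatment arm as independent (class) variable and with V2 HbA1c and site (class) as covariates. The A − B contrast is tested first, and the A − C contrast only if A − B is significant.*

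This follows the sponsor's own DTQ model and takes both contrasts from one fit. Reporting the adjusted differences with 95% confidence intervals would be a sensible addition, but it is optional and not part of the correction.

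The cost is one sentence of SAP text. No new data are needed, and the design, sample size and conduct stay as they are. It is best made before the HbA1c comparison is run; if that has already happened, the report should state the model actually used.

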#### **6.8.1.3. Impact of Solo Device Version**

The device version used the majority of time during the last two weeks before completion of a given questionnaire will be listed for each subject using the Accu-Chek® Solo micropump and tabulated by version and visit.

#### **6.8.1.4. Examination of Insertion Sites**

Answers to the “examination of insertion site” questions will be listed by visit and question and will be tabulated by treatment group and visit.

### 6.8.2. Diabetes Medication Information

The following diabetes related characteristics will be listed by subject and visit, and tabulated by treatment. For a given visit, always the information from the last change before that visit will be utilized in order to tabulate and list the status at this visit, not the changes.

Additionally, differences between baseline values and V4, between V4 and V5, and between baseline and V5 will be tabulated.

The summary tables for medical history of diabetes will show absolute and relative frequencies for

- Basal insulin used
- Bolus insulin used
- as well as the continuous variable statistics as defined in section 0 for the following variables
- Basal and Bolus doses
- Bolus count

The following information will be listed for each patient and each timepoint specified by the patient

- Insulin sensitivity, glucose target range, carbohydrate factor and the according time range
- Type of basal insulin
- Type of bolus insulin
- Insulin-to-carbohydrate ratio

### 6.8.3. Diabetes and Concomitant Medication

Previous and concomitant medications (separated for diabetes and for other indications) will be tabulated by study arm and listed by subject.

#### 6.8.4. Blood Glucose Data

As described in section 4.2.2, blood glucose data originating from spot measurement and from CGM differ substantially in their evaluable properties. Some analyses are only meaningful for subjects performing spot measurement, some only for subjects utilizing CGM and some for both. And for subjects utilizing both, the results from some analyses may at least be questionable, even though they are possible. The frequency of spot measurements may for example be misleading if a subject is using both spot and CGM measuring, simply because there is no need for frequent spot measurements if subjects use a CGM data and BGM frequency may thus be biased for these subjects.

Data will be listed and tabulated by study arm and visit. Additionally, differences between V4 and V5 will also be tabulated. Tabulation will follow the description in section 0. Because there are marginal but nevertheless important differences in the analysis of BG and data resulting from spot and CGM measurements, the analysis is described in detail in sections 6.8.4.1 and 6.8.4.2

##### 6.8.4.1. Subjects with BG data only

The following properties will be analyzed.

- Frequency of BG measurements
- Fraction of measurements in the following ranges
  - < 54 mg/dL
  - $\geq 54$  mg/dL and < 70 mg/dL
  - $\geq 70$  mg/dL and  $\leq 180$  mg/dL
  - > 180 mg/dL and < 250 mg/dL
  - > 250 mg/DL
- Additionally, the fraction of measurements in the following ranges will be tabulated for each treatment group.
  - < 70 mg/dL
  - $\geq 70$  mg/dL and < 140 mg/dL

- > 140 mg/dL

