### **9.2.1 Asymptomatic Hypoglycemic Episode**

An asymptomatic hypoglycemic episode is defined as a low blood glucose reading below 70 mg/dL (3.9 mmol/L) without symptoms and is considered as a non-captured expected AE described in Section 9.3.1.2.

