### **9.2.4 Hyperglycemic Episode**

Hyperglycemia is defined as high blood glucose readings, a recommended threshold to intervene could be defined as values above 250 mg/dL (13.9 mmol/L). However, investigators should consider the condition of the individual subject.

Only hyperglycemia episodes in combination with medical intervention or additional diagnostic procedures have to be documented as AE in the eCRF, as described in Section 9.3.1.1.

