#### 3.2. Data conversion

In cases where the eCRF allows entering data in different units, respective data will be converted and the converted form will be used for analysis and for reporting.

- HbA1c will be converted to “%”
- BG values will be converted to mg/dL
- Length will be converted to “cm”
- Weight will be converted to “kg”

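### The glucose range lists in SAP 6.8.4.1 and 6.8.4.2 leave readings of exactly 250 mg/dL (five-range set) and exactly 140 mg/dL (three-range set) in no category

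*SAP*

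**What the plan says.** SAP 6.8.4.1 (meter data only) and SAP 6.8.4.2 (CGM data) give the same two lists, under the instruction "Fraction of measurements in the following ranges" and a companion line for the second list.

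- Five-range set, in mg/dL: below 54; 54 up to but excluding 70; 70 to 180 inclusive; "> 180 mg/dL and < 250 mg/dL"; above 250.
- Three-range set, in mg/dL: below 70; from 70 inclusive, "mg/dL and < 140 mg/dL"; above 140.

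SAP 6.8.4 asks for these by study arm and visit, with differences between Visit 4 and Visit 5. On units, SAP 3.2 says "BG values will be converted to mg/dL", for data that the eCRF accepts in more than one unit. It gives no conversion factor, rounding rule or precision.

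The protocol places hyperglycaemia at "values above 250 mg/dL (13.9 mmol/L") in section 9.2.4, and asymptomatic hypoglycaemia at readings "below 70 mg/dL (3.9 mmol/L") in section 9.2.1.

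**The concern.** A set of ranges used to report fractions should place every reading in exactly one range. The cuts at 54, 70 and 180 do this, because the boundary value is assigned to one side. The cut at 250 in the first set and the cut at 140 in the second are strict on both sides, so the boundary value is assigned to neither.

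A programmer who follows the text drops those readings. If the denominator is all readings, the fractions fall short of 100%. If it is only the classified readings, every fraction is slightly inflated. SAP 6.3 defines percentage denominators in terms of patients, so it does not settle the matter for readings. A programmer who notices the gap must choose a side without a written rule. One of the two cuts is also the level that the protocol uses to describe hyperglycaemia, and frequency of hyperglycaemia is a listed secondary parameter.

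**Working it through.** The plan states no figure that can be reproduced here. The check is logical first, then a rough sizing.

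**1. Which values are unclassified?** Every whole number from 20 to 600 mg/dL was tested for membership in exactly one range of each set.

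| Set | Unclassified as written | After closing one side |
|---|---|---|
| Five ranges | 250 only | none |
| Three ranges | 140 only | none |

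Each set misses one value, not two: 140 lies in the 70-180 range of the first set, and 250 lies in the top range of the second.

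**2. How many readings is that?** The documents give no distribution, so a lognormal is assumed with mean m of 150 to 210 and SD s of 50 to 80 mg/dL, recorded in whole mg/dL. With σ² = ln(1 + (s/m)²) and μ = ln m − σ²/2, the loss at cut v is P(v − 0.5 < X < v + 0.5).

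Example, m = 170 and s = 70: σ² = ln(1 + 0.1696) = 0.157, σ = 0.396, μ = 5.136 − 0.078 = 5.057.
- At 140: z = (4.942 − 5.057)/0.396 = −0.29, so the density is 0.382/(140 × 0.396) = 0.0069 per mg/dL, or 0.69% of readings.
- At 250: z = (5.521 − 5.057)/0.396 = 1.17, so the density is 0.201/(250 × 0.396) = 0.0020, or 0.20%.

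Across all the assumed settings:

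| Cut | Loss, whole mg/dL | Set then sums to |
|---|---|---|
| 250 | 0.11% to 0.47% | 99.53% to 99.89% |
| 140 | 0.33% to 0.88% | 99.12% to 99.67% |

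If unclassified readings are instead removed from the denominator, the worst case multiplies every other fraction by 1/(1 − 0.0088) = 1.009.

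**3. What happens to mmol/L readings?** Assume a display in 0.1 mmol/L steps. The protocol's own pairs imply factors of 250/13.9 = 17.99 and 70/3.9 = 17.95; these are rounded equivalents and do not fix a factor. Three factors were tried.

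| Factor | 7.8 mmol/L | 13.9 mmol/L |
|---|---|---|
| 18 | 140.4 | 250.2 |
| 18.0156 | 140.52 | 250.42 |
| 18.0182 | 140.54 | 250.45 |

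- Unrounded: no 0.1-step reading equals 140 or 250, so nothing is lost.
- Rounded to the nearest whole number: 13.9 becomes 250 and is lost under all three factors; 7.8 becomes 140 and is lost with factor 18 only, and becomes 141 and is kept with the other two.
- Truncated: both are lost. Rounded up: neither is.

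Where a step does land on a cut, it spans about 0.1 × 18 = 1.8 mg/dL, so the loss is about 1.8 times the whole-mg/dL figure: 0.19% to 0.84% at 250 and 0.61% to 1.57% at 140 under the same assumed distributions.

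**The case against.** The strongest reply is that this is a slip of notation with almost no consequence. The tables are descriptive and secondary. SAP 6.1 rules out testing unless it is specified, and SAP 6.8.4 specifies none. Hypoglycaemia and hyperglycaemia events are also tabulated in SAP 6.9, and hypoglycaemia episodes in SAP 6.12, so these fractions are not the only source. All of that stands, and it limits the importance of the point. It does not make the rule correct: the text as written leaves readings out.

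The gap is unlikely to come from the PDF conversion, because the inclusive signs survive at neighbouring cuts and the same pattern appears in both sections.

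A reader might infer more than the documents support:

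- *That mmol/L devices lose more readings.* They may lose more, fewer or none, depending on a factor and rounding rule that SAP 3.2 does not give. It is also unclear whether SAP 3.2, which concerns eCRF entry, governs glucose readings downloaded from devices.
- *That the loss differs between countries or arms.* Neither document ties a unit to a country, and nothing shows an imbalance between arms.
- *That hypoglycaemia fractions are affected.* The ranges below 54, from 54 to 70 and below 70 have no gap. They would shift only through the denominator, if unclassified readings were removed from it.

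**Conclusion.** The point holds, and it is minor. In both sections the five-range set omits exactly 250 mg/dL and the three-range set omits exactly 140 mg/dL, so each set of fractions can sum to less than 100%. That follows from the text alone. The size does not: roughly 0.1-0.5% of readings at 250 and 0.3-0.9% at 140 rests on assumed lognormal distributions and on readings recorded in whole mg/dL. For mmol/L data the documents support only the statement that the effect is undetermined, and is nil if converted values are left unrounded. The primary DTQ analysis does not use these ranges.

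**What to change.** In both SAP 6.8.4.1 and SAP 6.8.4.2:

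- make the fourth range of the first set >180 and ≤250 mg/dL, leaving the top range at >250;
- make the middle range of the second set ≥70 and ≤140 mg/dL, leaving the top range at >140.

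The first edit keeps the top range consistent with the wording of protocol 9.2.4 and changes no clinical threshold. For 140, either side would close the gap; this choice leaves the top range as it is.

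In SAP 3.2, state the conversion factor, say whether it applies to downloaded device readings, and require classification on unrounded converted values.

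The cost is one comparison sign per list (four in all) plus a sentence in SAP 3.2. No new data and no change to study conduct are needed.
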